3.2 Secondary Objectives

- 1) Assess the socio-economic status and geographic origin of patients.
- 2) Assess the number of enquiries to webpage and completion of registration forms.

4 CONSENT

Informed consent will be obtained from participants when onboarding to the clinical service for treatment with a CBMP. If they subsequently decide to join the feasibility study, then they will sign a separate consent form for the study.

5 ELIGIBILITY CRITERIA

5.1 Inclusion Criteria

1. A consented patient at the clinic;
2. Male or female 18-85 years old;
3. Diagnosed with chronic non-cancer pain;
4. Is currently receiving standard of care but still has pain, has completed standard of care pain treatment, does not want standard of care treatment, or standard of care is contraindicated. An inadequate response is defined as the subject receiving standard analgesic agents and still has pain, has unpleasant side effects or wishes to reduce their intake of standard of care analgesic agents, e.g. a subject receiving opioids who wishes to dose reduce in light of the “opioid crisis”;
5. Despite being on or having received standard of care and has still pain (>3 on the Pain NRS); and
6. Signed and dated consent form from the patient.

7.2 Exclusion Criteria

1. Pregnant or lactating females or females who are planning a pregnancy during the study;
2. Positive pregnancy test at time of joining the clinic;
3. Major organ failure, renal, lung or liver failure;
4. Participants having active liver disease or unexplained persistent elevation of serum transaminases > 3 times the upper limit of normal;
5. Participants with a creatinine clearance < 60mL/min;
6. History of cardiac or respiratory failure;
7. History of recent myocardial infarction or poorly controlled ischaemic heart disease;
8. Severe respiratory disease (e.g., GOLD 3 for COPD or asthmatics requiring high doses of oral corticosteroids);
9. History or presence of alcohol or substance abuse, including analgesics used as standard of care;
10. Participation in a clinical trial of an investigational medicinal product;
11. With any known or suspected history or family history of schizophrenia, or other psychotic illness; history of severe personality disorder or other significant psychiatric disorder disorders other than depression associated with their underlying condition;
12. Known hypersensitivity to cannabis or allergy to cannabis or CBMP; and
13. Currently taking cannabis and does not agree to a 3 week wash out period.

6 DATA HANDLING AND MANAGEMENT

Information related to feasibility study will be extracted from the participating clinical sites electronic health record (EHR) system which will contain all the relevant patient information, prescribing information, safety information and questionnaires completed. At the end of the feasibility study information on the relevant domains will be extracted and collated into a feasibility study report.

7 MONITORING AND AUDITING

The Chief Investigator will ensure there are adequate quality controls in place for conducting the feasibility study by the Sponsor. This will include adherence to the protocol and ensuring adequate data quality.

The Chief Investigator will inform the Sponsor should he/she have concerns which have arisen from monitoring activities, and/or if there are problems with oversight/monitoring procedures.

8 TRAINING

The Chief Investigator will review and provide assurances of the training and experience of all research-relevant staff working within the Sponsor. All staff involved in the study will have up to date GCP and other training necessary for working in such a clinic.

Coordinating Trial Centre	Harley Street (CPC) Limited	
Duration of trial	3 years with a minimal planned sample size of 5000 participants who have completed at least 12 months of treatment with CBMP.	
Objectives	To determine the safety and the effectiveness of a medical cannabis treatment for moderate to severe chronic non-cancer pain in a real world setting on pain numerical rating scores (NRS) scores, quality of life measures, sleep scores, personal wellbeing, global impression of change and changes in the dosing of concomitant analgesic treatments, compared with appropriate matched controls receiving opioids and/or other neuropathic pain relief. To determine the tolerability of a medical cannabis treatment in patients by assessing psychological morbidity such as anxiety and effects on gut function, and dizziness measurements.	
Rationale	Medicinal cannabis has recently been re-categorised from Schedule 1 to Schedule 2 in the misuse of drugs regulations, meaning it is recognised to have medical applications and can now be prescribed to patients suffering from conditions where clinical evidence exists for its use. One of the conditions where the scientific literature contains evidence for the utility of medicinal cannabis is chronic non-cancer pain. Further data on effectiveness and tolerability is required and synthesis of this data is the main purpose of this study. Globally, three types of medical cannabis products are commonly used to treat chronic non-cancer pain. These products contain either a high, medium or low content of THC balanced by reciprocal ratios of CBD. We believe that the evidence base indicates that whole flower products with balanced THC and CBD content and levels of other phytochemicals unaffected by extraction, give the maximum levels of efficacy. However, more evidence is needed on the use of these forms of medical cannabis to assess efficacy and tolerability. In addition, data will be collected on the concomitant dosing of medications such as opioids and anti-neuropathic adjuvant analgesics, as part of a patient's standard of care, thereby enabling the impact of medicinal cannabis on the use of standard of care treatment to be assessed.	


Design
	
This trial will be conducted in a single private health clinic, staffed by clinicians experienced in prescribing and managing the use of medicinal cannabis or who will be trained to do so. The trial will use established treatment protocols which originate from experienced healthcare practitioners working at established medical cannabis clinics in comparable healthcare environments to the UK. Participant's data will be collected as they are treated.
 
The trial is an open-label, real-world study reporting on the treatment outcomes across a range of chronic non-cancer pain disorders.
 
This is a prospective trial to determine the effects of medical cannabis ("Treatment") in chronic non-cancer pain subjects on:
 
 • Pain NRS • Quality of Life (QoL) • Sleep quality NRS • Anxiety NRS • Fatigue NRS • Nausea NRS • Depression NRS • Shortness of breath NRS • Dizziness (NRS) • Appetite (NRS) • Global Impression of Change (since commencing treatment) • Personal Wellbeing Score (NRS) • Changes in concomitant analgesic medication use 
and to assess the safety and tolerability of adding medicinal cannabis to the subject's standard of care.

Planned number of participants
	
Planned sample size of 5000 participants.

Enrolment criteria
	
Inclusion criteria
 
 1. Male or female 18-85 years old; 2. Diagnosed with chronic non-cancer pain and; 3. A consented patient at the Harley Street (CPC) clinic 4. Is receiving standard of care therapy with inadequate response or has completed standard of care treatment, does not want standard of care treatment, or standard of care is contraindicated. An inadequate response is defined as the subject receiving standard analgesic agents and still has pain, has unpleasant side effects or wishes to reduce their intake of standard of care analgesic agents, e.g. a subject receiving opioids who wishes to dose reduce in light of the "opioid

	
crisis".
 
 4. Despite being on or having standard of care and still has pain (>3 on the Pain NRS); and 5. Signed and dated written informed consent from the subject. 
Exclusion criteria
 
 1. Pregnant or lactating females or females who are planning a pregnancy during the study; 2. Positive pregnancy test at screening; 3. Major organ failure, renal, lung and liver failure; 4. Participants having active liver disease or unexplained persistent elevation of serum transaminases > 3 times the upper limit of normal; 5. Participants with a creatinine clearance < 60mL/min; 6. History of cardiac or respiratory failure; 7. History of recent myocardial infarction or poorly controlled ischaemic heart disease; 8. Severe respiratory disease (e.g., GOLD 3 for COPD or asthmatics requiring high doses of oral corticosteroids). 9. History or presence of alcohol or substance abuse, including analgesics used as standard of care. 10. Participation in a clinical trial of an investigational medicinal product; 11. With any known or suspected history or family history of schizophrenia, or other psychotic illness; history of severe personality disorder or other significant psychiatric disorder disorders other than depression associated with their underlying condition. 12. Known hypersensitivity to cannabis or allergy to cannabis or CBMP and 13. Direct employee of the study site.

Test product, dosage and mode of administration
	
The treatment regimen is as follows. In addition to standard of care management provided by their regular health care practitioner, participants will receive defined doses of inhaled CBMP namely Equipose 8-8 with a balanced ratio of THC and CBD as a dried cannabis flower.
 
Inhaled delivery
 
Cannabis flower containing mid and balanced levels of THC and CBD (Equipose 8-8), will be vaporised using a CE marked, handheld device with dose counting and Bluetooth connectivity to a smart device (Ryah).
 
Dosing will be recorded by the study participant entering their data into the ePRO data collection system through an application on their mobile phone. Participants will receive prompts to enter data and must do so to continue in the study.

Duration of treatment
	
3 years


Criteria for evaluation (Outcome variables)
	
Effectiveness:
 
Primary variables (comparable to matched controls):
 
 • Pain scores (NRS) summated and by pain types. 
Secondary variables (not comparable to matched controls):
 
 • Quality of life scores; 12 item short form health survey (SF-12), summated and by pain type • Sleep quality scores (NRS) • Anxiety (NRS) • Depression (NRS) • Fatigue (NRS) • Appetite (NRS) • Nausea NRS • Wellbeing score (NRS) • Global impression of change • Concomitant use of pain medications (doses per subject per week), summated and by pain type. In the case of opioids daily opioid uptake will be converted to morphine equivalent daily dose (MEDD) 
Safety and tolerability
 
Daily analysis of THC specific effects:
 
 • Anxiety (NRS), • Drowsiness (NRS) • Dizziness (NRS) • Shortness of breath (NRS) • Adverse events reported

Statistical considerations
	
Tabulations will be produced for appropriate effectiveness and safety parameters. For categorical variables, summary tabulations of the number and percentage of participants within each category (with a category for missing data where applicable) of the parameter will be presented. For continuous variables, the number of participants, mean, standard deviation (SD), median, minimum, and maximum values will be presented. Statistics may be presented for cohorts of interest (e.g. by subtypes of chronic pain) if sample size permits.
 
Inferential statistical methods will only be employed to highlight data of interest. Any p-values will be interpreted descriptively, and 95% confidence intervals (CIs) will be presented as appropriate.
 
The analysis of effectiveness will be controlled by comparison with matched controls identified from a database of comparable subjects with chronic non-malignant pain. In order to reduce bias and to balance the distribution of covariates in the treated and control groups, multiple regression analysis will be used, adjusting for potential confounders. Matching methods such as propensity scoring methods may also be used.

	
Statistical analysis, data listings, graphs and summary tables will be produced using SAS®, version 9.2 or above.
 
Full details, including the use of the matched control database(s), of the interim and final statistical analyses to be performed will be described in detail in the Statistical Analysis Plan (SAP).

--	---

DRAFT

Table 1-1: Schedule of Assessments

	Initiation visit Day 0 (Baseline)	Daily data collection	Weekly data collection	Monthly data collection	Follow up visits (every 3 months ^a)
Pre-read of patient information sheet and informed consent document	X				
Written Informed Consent	X				
Check of inclusion/exclusion criteria	X				
Demographic data	X				
Medical history	X				X
Standard of care medication (number of doses given in previous period of time)	X		X		X
Site of pain reported in NRS	X		X		X
Additional efficacy assessments			X		
Quality of life score	X				X
Blood reports ^b	X				X
Genetic test for cannabis tolerance validation study	X				
Continuous cannabis intolerance assessments: red flags		X			X
Overall assessment of efficacy and tolerability			X		X
Scan or additional tests ^b	X				X
Determination of state of disease	X				X
Adverse events	X	X	X		X
Prescription and treatment regimen compliance	X		X		X

a. Follow-up visit can be done in person or over the phone. If available.

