6. INVESTIGATIONAL PLAN

6.1 Overall study design and plan

This is a non-randomised, non-blinded single arm real world data collection study investigating the safety, tolerability and effectiveness of medicinal cannabis in chronic non-cancer pain subjects. The study will be conducted in a CBMP treatment clinic that has staff experienced at administering and managing the use of CBMP in its current unlicensed status. At time of enrolment, baseline data will be provided by the participant's health care team who is managing their chronic non-cancer pain (to current standard of care) and collected at the clinical study site. This will provide information on the type of chronic non-cancer pain the subject has (including relevant investigations previously conducted) and the types of drugs and non-pharmacological interventions that the subject is receiving or has received. The standard of care treatment and patient management will be determined by the treating physician. All study treatments and/or any change to treatment or management of the disease that occur throughout participation in the study will be recorded as well as being communicated to the subject's GP. Data will be collected either by the Physician during the study visit or via real time collection via an application (ePRO) provided to the subject. Data will be collected retrospectively and prospectively. A sample size of 5000 participants is planned.

[figure not shown]

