6.7 Effectiveness, tolerability and safety measurements

6.7.1 Effectiveness measurements

Change from baseline in pain intensity (pain NRS).

Change from baseline in quality of life measure (SF-12)

Change from baseline in well-being (well-being NRS)

Change from baseline in fatigue (fatigue NRS)

Change from baseline in nausea (nausea NRS)

Change from baseline in depression (depression NRS)
Change from baseline in anxiety (anxiety NRS)
Change from baseline in appetite (appetite NRS)
Change from baseline in sleep quality (sleep NRS)
Change from baseline in use of concomitant pain medications
Patient's global impression of change (PGIC)

Generally, these quarterly reports compare the results to the previous quarterly results and the Specialist can make comments about the changes from the previous period.

Numerical data will be collated and reports made on the baseline changes for pain, QoL, well-being, fatigue, nausea, depression, appetite, sleep quality, anxiety, global impression of change and concomitant medication, to define whether the subject has received benefit.

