9. STATISTICAL METHODS AND DETERMINATION OF SAMPLE SIZE

9.1 General considerations

The aim of the study is to evaluate whether a medical cannabis treatment in addition to standard of care is beneficial with regards to pain scores, quality of life measures, sleep scores, changes in concomitant medication use, subject's global impression of change and general wellbeing score, as well as being safe and tolerable. The study is a non-randomised, non-blinded, single arm study with comparisons being made against matched control database(s) where available and applicable.

There are many causes of chronic pain, which can be described as either neuropathic or non-neuropathic. In addition to those two main subtypes, there are 10 further subtypes which are as follows: systemic inflammatory disease, osteoarthritis, lower back pain, inflammatory bowel pain, neurogenic pain, post cancer pain, post trauma pain, psychogenic pain, genitourinary pain and vascular pain. These pain types will be recruited into both the CANPAIN cohort and matched cohorts.

The use of matched controls instead of a randomised control design is the best approach to studying medicinal cannabis due to the inherent difficulties of blinding trial subjects to the effects of cannabis. Protocol designs for the study of medicinal cannabis have been recently reviewed in a BMJ editorial (Freeman and Morgan 2019) which support the use study designs such as ours in the generation of evidence in medicinal cannabis use. Subjects in the active and control cohorts will be matched on a range of demographics, socio-economic, pain, and health related variables (see response to comment 1d). Certain covariates (such as gender) may be considered for exact matching if appropriate. Subjects will be matched using an optimal matching algorithm. For the primary analyses, a 1-1 matching algorithm will be used. At a predefined interval (12 months), a multiple regression analysis will be undertaken on subjects in the matched control cohort to assess which co-variables (e.g. categories of standard of care, pain type or location of pain). are important for the matching process with the CANPAIN cohort. Subgroups of special interest include type of pain, inclusion of gabapentinoids, age and gender. Subgroups of exploratory interest include but are not limited to, standard of care, site of pain and prior cannabis use. These will be fully defined in the SAP.

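### Non-opioid analgesic use is measured only by a dose count, which misses changes in strength, and the planned opioid morphine equivalent has no named strength data behind it

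*Protocol*

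**What the plan says.** All the relevant text is in the draft CANPAIN protocol attached as Appendix 1.

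- **Aim.** The synopsis Objectives row refers to "changes in the dosing of concomitant analgesic treatments". The Rationale row adds that "data will be collected on the concomitant dosing of medications such as opioids and anti-neuropathic adjuvant analgesics", so both opioids and non-opioids are in scope. Section 5 lists change in concomitant medicine as a secondary objective.
- **Unit.** The Criteria for evaluation row gives "Concomitant use of pain medications (doses per subject per week), summated and by pain type". The next sentence treats one class separately: "In the case of opioids daily opioid uptake will be converted to morphine equivalent daily dose (MEDD".
- **Collection.** The Table 1-1 row for other analgesics is "Standard of care medication (number of doses given in previous period of time", marked at baseline, weekly and at the three-monthly follow-up. The list of weekly assessments in section 6.6.1 has no medication item.
- **Endpoint restated.** Section 6.7.1 has "Change from baseline in use of concomitant pain medications", with no unit.
- **Other recording.** Section 6.1 says that "any change to treatment or management of the disease that occur throughout participation in the study will be recorded". It does not mention strength or milligrams.

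**The concern.** The aim is a change in dosing, that is, in how much analgesic patients take. The unit and the collection item for non-opioids are a count of how often they take it. The two agree only if the strength of each dose stays fixed. Strength may be lowered in a taper, or may change when a patient moves to a form taken more or less often.

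Inclusion criterion 4 admits patients who wish to reduce their standard analgesics, so reductions in dose are to be expected. If they occur through strength, the count can show no sparing where the amount fell. If they occur through a change of form, it can show sparing, or an increase, where nothing changed. A statistical analysis plan can refine a derivation, but it cannot recover strength that was never collected.

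**Working it through.** The documents give no figure for this outcome, so there is nothing of the plan's own to reproduce. The check is arithmetic on assumed regimens. These only illustrate the scoring; they are not taken from the documents and are not treatment suggestions.

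**Inputs.** From the protocol: the count unit and the morphine-equivalent rule (synopsis, Criteria for evaluation) and the collection item (Table 1-1). Assumed: the regimens below, and an oral morphine conversion factor of 1.

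**Formulas.**
- Doses per week = 7 × doses per day.
- Weekly amount = doses per week × mg per dose.
- Morphine equivalent daily dose = doses per day × mg per dose × conversion factor.

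If frequency changes by a factor f and strength by a factor s, the amount changes by f × s but the count changes by f alone. The count is therefore right only when s = 1.

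**Non-opioids (count only)**

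| Change | Doses/week | Scored | mg/week | True |
|---|---|---|---|---|
| 3 × 600 mg/day to 3 × 300 mg/day | 21 to 21 | 0% | 12,600 to 6,300 | −50% |
| 4 × 100 mg/day to 2 × 200 mg/day | 28 to 14 | −50% | 2,800 to 2,800 | 0% |
| 2 × 200 mg/day to 4 × 100 mg/day | 14 to 28 | +100% | 2,800 to 2,800 | 0% |

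The third row reverses the second and shows that the error can go either way.

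**Opioids (count and morphine equivalent)**

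| Change | Doses/week | Count | Equivalent, mg/day | Scored on equivalent |
|---|---|---|---|---|
| 6 × 10 mg/day to 6 × 5 mg/day | 42 to 42 | 0% | 60 to 30 | −50% |
| 6 × 10 mg/day to 2 × 30 mg/day | 42 to 14 | −66.7% | 60 to 60 | 0% |

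The morphine equivalent scores both opioid cases correctly. It needs mg per dose and the identity of the drug, however, and the Table 1-1 row names neither. Nor does the synopsis say whether opioid doses also stay in the weekly count, where both errors would return.

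**The case against.** Four objections carry weight.

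1. **Opioids already have an amount-based measure.** This stands. A reader might infer that the whole endpoint is a dose count that can hide a halved opioid intake. The sentence on morphine equivalents rules that out for opioids, provided the data exist to compute it. It matters because the example in inclusion criterion 4 and the analgesic-sparing rationale in section 4.1.1 both concern opioids.

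2. **Two further criticisms are tempting but unsupported.** One is that tablets of different drugs are added together. The same table cell uses summated in the same way for pain scores and SF-12, where it most naturally means overall as well as by pain type; adding across drugs is not established. The other is that gabapentinoids need an amount because section 9.1 singles them out. The text is "Subgroups of special interest include type of pain, inclusion of gabapentinoids, age and gender", which makes their use a grouping factor, not an outcome.

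3. **A schedule row is not a field specification.** Section 8.1 leaves the list of data fields to the sponsor. Sections 6.1, 6.2 and 6.6.1 provide for baseline drug types, recorded treatment changes, NHS data on standard care and three-monthly treatment reviews. Strength might be held in one of these, so it cannot be said that it will not be collected. But none of them names strength or is tied to this outcome, and the stated unit for non-opioids would remain a count even if strength were on file.

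4. **The outcome is minor.** It is one of many secondary variables. Section 9.5.1.1 plans descriptive statistics for it, and section 9.1 reads any p-values descriptively. None of the feasibility objectives in sections 3.1 and 3.2 uses it. This limits the importance of the point but does not make the measure valid.

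**Conclusion.** The point holds for non-opioid analgesics: the stated unit and the scheduled item measure frequency, not amount, and so do not measure the stated aim. In the illustrations the error is 50 percentage points for a halved strength (0% scored, −50% true). For a same-amount change in frequency it runs from 50 points too low to 100 points too high. How often such changes would occur is unknown; the documents give no data on it.

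For opioids the planned measure is sound. What is missing is a named source for drug and strength, and a statement that the morphine equivalent takes the place of the count.

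This should be corrected before the main study, but it does not threaten the primary pain comparison or the feasibility study's own conclusions. The conclusion assumes that doses means a number of administrations, as the wording of Table 1-1 indicates.

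**What to change.** 1. In Table 1-1 and the weekly electronic item, record drug, strength and number taken for each standard-of-care analgesic. Pre-fill the list from the Day 0 medication record so that patients confirm or edit it. Add the item to the weekly list in section 6.6.1.
2. In the synopsis and section 6.7.1, define the outcome for non-opioids as change from baseline in weekly milligrams per drug or class. For opioids, define it as change in morphine equivalent daily dose, and state that this replaces the dose count.
3. No separate change is needed for controls: section 6.2 already has the control data mirror the CANPAIN data except for tolerability.

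**Cost.** Data entry is slightly longer, mainly for patients on several analgesics. The burden is worth checking, because section 6.5.1 makes further use of the device depend on completing required entries. Section 2 of the feasibility protocol says that the clinical information patients provide follows Appendix 1, and section 3.1 (Domain 3) assesses ease of answering and questionnaire fatigue. The revised item can therefore be tried there first. The change concerns measurement only and alters no treatment.
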